2.2.3 Exploratory objective

To investigate the effects of NP-120 (20 and 40 mg TID) on lung function, health status, and SARS-CoV-2 RNA status in hospitalized patients with COVID-19 disease.

2.2.4 Safety objective

To study the safety of NP-120 (20 and 40 mg TID) in hospitalized patients with COVID-19 disease.

2.3 Endpoints

2.3.1 Primary endpoint

Patient clinical status (on the WHO 7-point ordinal scale) at day 15 in IP versus SOC control group patients:

1. Not hospitalized, no limitations on activities
2. Not hospitalized, limitation on activities
3. Hospitalized, not requiring supplemental oxygen
4. Hospitalized, requiring supplemental oxygen
5. Hospitalized, on non-invasive ventilation or high flow oxygen devices
6. Hospitalized, on invasive mechanical ventilation or ECMO
7. Death

2.3.2 Secondary endpoints

- Status on an ordinal scale assessed daily while hospitalized and on days 15 and 28 in IP versus control group patients
- NEWS assessed days 3, 5, 8, 11 while hospitalized and on days 15 and 29 in IP versus control group patients
- Rate of mechanical ventilation in IP versus control group patients
- Duration of mechanical ventilation (if applicable) in IP versus control group patients
- Duration of supplemental oxygen in IP versus control group patients
- Time to return to SpO₂ > 94% on room air
- Duration in ICU (if applicable) in IP versus control group patients
- Rate of Mortality in IP versus control group patients
- Duration of hospitalization in IP versus control group patients
- Time to discharge in IP versus control group patients
- Effect on the rate of change of partial pressure of oxygen (PaO₂) and PaO₂/FiO₂ ratio taken at baseline and measured once daily up to 2 weeks of treatment in IP versus control group patients

2.3.3 Exploratory efficacy endpoints

- Changes in the extent of dyspnea from baseline, using a Likert scale, at Days 2, 4, 8, and 14 in IP versus control group
[Likert scale: The patient grades his/her current breathing compared to when he/she first started the study (from -3 to 3). "0" = no change, "1" = minimally better, "2" = moderately better, "3" = markedly better, "-1" = minimally worse, "-2" = moderately worse, "-3" = markedly worse]. For the first questionnaire (at baseline), the patient compares their current shortness of breath to their shortness of breath when they are well.
- Rate of change to patient's experience of cough (Visual analog scale [VAS]) at Days 2, 4, 8, and 14 in IP versus control group
VAS: The patient draws a vertical line on an axial graph (from 0 to 100) to show the degree of how he/she feels about coughing. The number "100" equals the worst coughing the patient has ever felt and the number "0" equals the best he/she has felt since baseline.
- Changes in D-dimer in IP versus control group
- Qualitative PCR for SARS-CoV-2 at baseline, days 5 (while hospitalized, and days 15 and 29 (if able to return to clinic or still hospitalized)
- Quantitative PCR (if available) for SARS-CoV-2 at baseline, days 5 (while hospitalized, and days 15 and 29 (if able to return to clinic or still hospitalized)

2.4 Safety Endpoints:

- Type, frequency, severity, and relationship of AEs to investigational product (IP)
- Number of patients who discontinue IP due to any AE
- Frequency of clinically significant changes in vital signs and/or laboratory findings

2.5 Sample Size

For the pilot phase, a sample of 150 patients (50 in Arm A, Arm B and SOC) will be recruited. To account for drop out of 10%, a total of 168 patients will be enrolled.

For the pivotal phase, A sample of 462 patients (231 in the SOC group and 231 in the active treatment group) achieves 90% power to detect a change in the log odds ratio of 0.5596 when the significance level (alpha) is 0.05 using a two-sided test. A log odds ratio of 0.5596 corresponds to an odds ratio of 1.75 comparing treatment to SOC. The sample size was estimated using the *Tests for Two Ordered Categorical Variables* module in PASS 14. To account for drop out of 10%, a total of 514 patients will be enrolled.

The sample size assumes that the distribution of patients on day 15 will be as shown in [Table 2](#), which is scenario 4 in the WHO master protocol (2020) for enrolled patients with moderate to severe disease under an odds ratio of 1.75.

Table 2 Distribution of Patients Across Outcome Categories at Day 15: SOC (WHO MP Scenario 4) and Treatment (Assuming OR of 1.75)

Outcome	Percent of Patients	
	SOC	Treatment
7. Death	2	1.0
6. Hospitalized & on mechanical ventilation or ECMO	1	0.6
5. Hospitalized & on non-invasive ventilation or high flow O2	2	1.2
4. Hospitalized & requires supplemental O2	5	3.03
3. Hospitalized not requiring supplemental O2	17	11.45
2. Not hospitalized but limitations on activities	36	31.90
1. Not hospitalized & no limitations on activities	37	50.70

2.6 Randomization

Static randomization using block size of 3 will be employed with stratification by site and age (<65 versus ≥65). Patients who withdraw from the study or are lost to follow-up after signing the informed consent form and randomization will not be replaced.

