## 1. PROTOCOL SYNOPSIS

**TITLE:** A Randomized Open Label Phase 2b/3 Study of the Safety and Efficacy of NP-120 (Ifenprodil) for the Treatment of Hospitalized Patients with Confirmed COVID-19 Disease

**TRIAL DESIGN:** Open-label, multi-center, randomized, parallel group study

This protocol is largely based on the recommendations of the [WHO R&D Blueprint Clinical Trials Expert Group COVID-19 Therapeutic Trial Synopsis](#), and associated [Master Protocol](#).

**NUMBER OF STUDY CENTERS:** Approximately 10

**STUDY LOCATION:** Canada, US, Australia, Philippines, Romania

**PHASE OF DEVELOPMENT:** 2b/3

**INDICATION:** Treatment of SARS-CoV-2 Infected Patients

**INVESTIGATIONAL PRODUCT:** NP-120 (Ifenprodil tartrate)

**STUDY RATIONALE:** NP-120 (Ifenprodil) is an N-methyl-D-Aspartate (NDMA) inhibitor that is specific for the NR2B subunit of the NMDA Receptor. The NMDA receptor, and specifically the NR2B subunit, is involved in glutamate signaling, and is expressed on both neutrophils and T cells. In the case of neutrophils, activation of the NMDA receptor can (1) result in expression of CD11b which targets neutrophils via ICAM-1 to areas of inflammation, and (2) trigger the autocrine release of glutamate. In the case of T-cells, activation of T cells via glutamate can cause (1) T cell proliferation and, (2) the release of cytokines. The activation of T cells and cytokine release can be blocked *in vitro* by the addition of Ifenprodil. As such it could be a potent anti-inflammatory agent.

Ifenprodil was discovered by a genome wide RNAi assay to uncover gene targets associated with cytoprotective activity against highly pathogenic H5N1 influenza, specifically by preserving cell viability *in vitro*. When tested in a murine model of H5N1, the drug at clinically relevant doses: (1) improved survivability from 0% at day 6 to 40% day 14 post-infection, (2) the drug significantly reduced edema and lung injury score and (3) reduced infiltrating T cells, neutrophils and NK cells and attenuated the ‘cytokine storm’. The mortality rate of H5N1 in humans is >50%, whereas the mortality rate of SARS-CoV-2 infected patients is < 5%, and both viruses cause acute lung injury and share similar pulmonary pathologies. NP-120 has also been shown to mediate anti-inflammatory responses and reduce pulmonary fibrosis in a murine model of idiopathic pulmonary fibrosis, a complication which can occur after a respiratory virus infection.

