## **4. STUDY DESIGN**

### **4.1 Overall Design**

This is a Phase 2b/3, multicenter, open label, randomized, parallel group study to evaluate the efficacy of Ifenprodil in patients with COVID-19 disease.

In the Phase 2b phase, patients will be randomized in a ratio of 1:1:1 to either a) 20 mg TID IP plus Standard of Care group, b) 40 mg TID IP plus Standard of Care or c) Standard of Care only group. Investigators will collectively enroll approximately 50 evaluable patients in each treatment group, for a total of 150 patients. Patients receive either oral Ifenprodil (20 or 40 mg TID) for up to 14 days in addition to Standard of Care, or Standard of Care only. The Standard of Care for each patient will be captured in the eCRF.

[figure not shown]
Randomization will be stratified by site, and age (<65 versus  $\geq 65$ ).

For Phase 2b, One interim statistical analysis will be performed on the primary endpoint of each arm after the first 75 patients have completed up to 2 weeks of treatment (Day 15). This analysis is being done to allow safety assessment and some snapshots of efficacy assessments as the trial progresses.

The Phase 2b study will also evaluate the different constructs of the ordinal scale (different days and different number of categories) by severity (severe vs. mild-moderate). Data from the Phase 2b study will be used to down select and prioritize the secondary endpoints. . The protocol would then be amended for the Phase 3 study to include the additional required number of patients to be recruited for the study to meet statistical significance in its primary endpoint.

An additional placebo arm will be added in the Phase 3 portion of the study. The number of participants to be enrolled in Phase 3 pivotal stage will be determined based upon the outcome of pilot Phase 2b stage of the study. Participants will be randomized to receive IP plus SOC, or Placebo plus SOC. Details will be outlined in a protocol amendment

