#### **4.4 Design Justification**

This study represents one of the first repurposed investigations of Ifenprodil in patients with COVID-19 disease. This study will provide information on the safety and clinical efficacy in the SARS-CoV-2 infected population prior to advancing to larger clinical trials, as well as provide critical information for the design of future studies in this population.

The purpose of this study is to determine whether Ifenprodil is effective and safe in the treatment of patients with COVID-19 disease. The primary measure of efficacy will be patient clinical status (on a 7-point ordinal scale) at day 15 in IP versus control group patients. This protocol is based on the recommendations of the [WHO R&D Blueprint Clinical Trials Expert Group](#).

The Phase 2b stage will be an open label study with patients, investigator, site and CRO staff aware of treatment received. The Phase 3 stage of the protocol will also include a placebo arm to allow for double-blinding.

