## **5.2 Exclusion Criteria**

1. Patients with vasodilatory shock, orthostatic hypotension, hypotension, or tachycardia at screening/baseline
2. Patients experiencing cerebral hemorrhage or cerebral infarction at baseline
3. ALT/AST > 5 times the upper limit of normal; Child-Pugh Score 10 to 15.
4. Stage 4 severe chronic kidney disease or requiring dialysis (i.e. eGFR < 30)
5. Patients on mechanical ventilation or extracorporeal membrane oxygenation (ECMO)
6. Patients taking droxidopa
7. Pregnant and lactating women and those planning to get pregnant
8. Known or suspected allergy to the trial drug or the relevant drugs given in the trial
9. Presence of other disease that may interfere with testing procedures or in the judgement of the Investigator may interfere with trial participation or may put the patient at risk when participating in this trial
10. Know inability of patient to comply with the protocol for the duration of the study
11. Involvement in a clinical research study within 4 weeks prior to screening and/or prior enrollment in the study or plan to participate in another interventional clinical trial during the study period. Participation in observational registry studies is permitted.

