## **5.3 Screening/Baseline/Randomization**

Screen failures are defined as patients who consent to participate in the clinical trial but are never subsequently enrolled. In this study, a patient can become a screen failure at any time during the screening visit (Visit 1), prior to randomization. In order to ensure transparent reporting of screen failure patients, meet the [Consolidated Standards of Reporting Trials \(CONSORT\)](#) publishing requirements, and respond to queries from Regulatory authorities, a minimal set of screen failure information is required including Demography, Screen Failure details, and Eligibility Criteria.

When a patient meets all eligibility requirements, study site personnel will consult the study database to obtain the patient's randomization number and treatment assignment.

Under no circumstances will patients randomized in the trial be permitted to be re-screened and randomized for a second time in this trial.

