2. PROJECT OVERVIEW

2.1 Study Design

This is a Phase 2b/3, multicenter, open label, randomized, parallel group study to evaluate the efficacy of Ifenprodil in patients with coronavirus disease of 2019 (COVID-19) disease.

In the Phase 2b phase, patients will be randomized in a ratio of 1:1:1 to either a) 20 mg TID IP plus Standard of Care group, b) 40 mg TID IP plus Standard of Care or c) Standard of Care only group. Investigators will collectively enroll approximately 50 evaluable patients in each treatment group, for a total of 150 patients. Patients receive either oral Ifenprodil (20 or 40 mg ter in die (TID)) for up to 14 days in addition to Standard of Care, or Standard of Care only. The Standard of Care (SOC) for each patient will be captured in the electronic clinical reporting form (eCRF).

Randomization will be stratified by site, and age (<65 versus ≥65).

For Phase 2b, one interim statistical analysis will be performed on selected efficacy endpoints and for safety for each arm after the first 75 patients have completed up to 2 weeks of treatment (Day 15). This analysis is being done to allow safety assessment and some snapshots of efficacy assessments as the trial progresses.

The Phase 2b study will also evaluate the different constructs of the ordinal scale (different days and different number of categories) by severity (severe vs. mild-moderate). Data from the Phase 2b study will be used to down select and prioritize the secondary endpoints. The protocol would then be amended for Phase 3 study to include the additional required number of patients to be recruited for the study to meet statistical significance in its primary endpoint.

An additional placebo arm will be added in the Phase 3 portion of the study. The number of participants to be enrolled in Phase 3 pivotal stage will be determined based upon the outcome of pilot Phase 2b stage of the study. Participants will be randomized to receive investigational product (IP) plus SOC, or Placebo plus SOC. Details will be outlined in a protocol amendment

Figure 1: Trial Design

[figure not shown]

Table 1 Schedule of Events

Trial Activity	Screening/Baseline/ Enrolment visit	Daily until hospital discharge	End of treatment	Follow-up period	
Day	1	2-14	15	29	60
Allowed window for visit (±)	-1 ^a		2	2	3
Visit	1		2 ^b	3	4
Informed consent	•				
Inclusion/exclusion criteria including confirmation of COVID-19 diagnosis	•				
Confirmation SARS-CoV- 2 ^h	•	•	•	•	
Pregnancy test	•				

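### A single fixed block of 3 within site-by-age strata lets open-label site staff who know or infer the block size deduce the last allocation in each block

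*SAP*

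**What the plan says.** SAP 2.6 gives the whole allocation method in one sentence: "Static randomization using block size of 3 will be employed with stratification by site and age", with age split at 65. SAP 2.1 says that "patients will be randomized in a ratio of 1:1:1 to either" ifenprodil 20 mg, ifenprodil 40 mg or SOC alone, with both active arms given on top of SOC. Protocol 4.1 names the same strata ("Randomization will be stratified by site, and age") but gives no block size.

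On blinding, Protocol 4.4 says: "The Phase 2b stage will be an open label study with patients, investigator, site and CRO staff aware of treatment received". On obtaining an assignment, Protocol 5.3 says that once eligibility is met "study site personnel will consult the study database to obtain the patient's randomization number and treatment assignment".

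Neither document describes varying block sizes or withholding the block size from sites. The primary model in SAP 11.1 contains treatment, age and site. Baseline WHO score is neither a model term nor a stratification factor.

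**The concern.** With three arms at 1:1:1, 3 is the smallest block possible. Because site is a stratum, each site sees both of its own sequences (under 65, and 65 or over) in full, and because the stage is open label it sees every past assignment. Drawing assignments from a database hides the list, but does not stop staff deducing the next entry from the previous two.

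Staff who can foresee an assignment have some room to act on it. Protocol 7.3.1 allows up to 24 hours between screening and randomization. Protocol 5.2 includes an exclusion for other disease that "in the judgement of the Investigator may interfere with trial participation". Eligible patients enter at WHO score 4 or 5 (Protocol 5.1), so they can differ in severity within a stratum.

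At stake is the comparability of the arms. If sicker or fitter patients were steered towards particular slots, the difference would pass into the day-15 odds ratio, and adjusting for site and age would not take it out. Phase 2b also feeds later decisions. Protocol 10.3 lists the target population, choice and timing of the primary endpoint, and number of scale categories as open to change for Phase 3. SAP 11.1 allows p-values below 0.05 to be treated as encouraging for the next stage.

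**Working it through.** **Inputs.** One block size of 3 (SAP 2.6); 1:1:1 to three arms (SAP 2.1); strata of site by two age groups (SAP 2.6, Protocol 4.1); number of centres "Approximately 10" (Protocol synopsis), hence about 10 × 2 = 20 strata; "a sample of 150 patients (50 in Arm A, Arm B and SOC) will be recruited", raised to 168 for 10% drop-out (SAP 2.5).

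**The plan's own figure.** The documents give no predictability figure. The enrolled total reproduces: 50/0.9 = 55.6, rounded up to 56 per arm, and 3 × 56 = 168.

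**Complete blocks of 3.** Take an observer who knows the block size and has seen the earlier allocations in the stratum.

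| Position in block | Chance of a correct guess | Exact arm certain | Active versus SOC certain |
|---|---|---|---|
| 1 | 1/3 | 0 | 0 |
| 2 | 1/2 | 0 | 1/3 (when the first patient was SOC) |
| 3 | 1 | 1 | 1 |
| Average | (1/3 + 1/2 + 1)/3 = 61.1% | 1/3 = 33.3% | (0 + 1/3 + 1)/3 = 4/9 = 44.4% |

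By chance alone, a guess is right 33.3% of the time.

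**Allowing for incomplete blocks.** Assume that 168 patients fall evenly at random over S strata. The patients left in an unfinished block (0, 1 or 2) then average very nearly 1 per stratum.

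- Completed blocks, and so patients whose exact arm is certain: (168 − S)/3. For S = 20 this is 148/3 = 49.3, or 29% of 168. For S = 10 it is 52.7, and for S = 30 it is 46.0.
- Active versus SOC certain: completed blocks × 4/3, plus S × 1/3 × 1/3 for strata that stop after a second patient. For S = 20 this is 65.8 + 2.2 = 68.0, or 40% of 168. For S = 10 it is 71.3, and for S = 30 it is 64.7.
- The ceiling for the exact arm, if every block filled, is 168/3 = 56 patients.

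**Alternatives.** The fixed sizes were enumerated. The mixed sizes were simulated over long sequences, for an observer who knows which sizes are in use but not their order.

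| Block scheme | Exact arm certain | Active versus SOC certain | Best-guess success |
|---|---|---|---|
| Fixed 3 | 33% | 44% | 61% |
| Fixed 6 | 20% | 29% | 56% |
| Random 3 or 6 | about 9% | about 13% | about 58% |
| Random 6 or 9 | about 5% | about 8% | about 54% |

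Varying the size removes most of the certain allocations. It lowers overall guessing only modestly.

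**The case against.** The strongest reply is that predictability is conditional. The block size appears in the SAP and not in the protocol text supplied, and nothing says that sites receive the SAP. Staff would have to infer it and keep track of each stratum. This stands as a condition on the finding, but it does not remove it: at an unblinded site, one of each arm in every three patients is a pattern that can be recognised.

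Second, the effect on the result is not shown. Assignments are released only after eligibility is met, and entry is confined to WHO scores 4 and 5, which narrows the scope for steering. This also stands. The documents show an opportunity, and offer no basis for putting a size on any bias.

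Third, SAP 11.1 calls this stage exploratory, and Protocol 4.4 plans Phase 3 with placebo and double-blinding. That limits the harm. It does not protect the Phase 3 choices that Phase 2b is meant to inform.

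Fourth, the change may not be as simple as a new list. Protocol 4.6 planned the first patient for the third quarter of 2020, while the SAP cites a protocol dated 16 November 2020 (SAP 1). Enrolment may have been under way when the SAP was written, although the actual start is not stated.

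A reader might infer that staff know every next allocation, or that the Phase 2b odds ratio is biased. The documents support neither. The first patient in a block is unpredictable, the exact arm of the second is never certain, and nothing indicates that anyone would act on the knowledge.

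**Conclusion.** The point holds as a design weakness that is cheap to reduce. For staff who know or infer the block size, the exact arm is certain for up to 33% of allocations, and active-versus-SOC status for up to 44%. Those are ceilings for complete blocks. About 29% and 40% (roughly 49 and 68 of 168 patients) is more realistic, assuming about 20 strata and even, random accrual. Across 30 to 10 strata the ranges are 46 to 53 patients and 65 to 71 patients.

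The predictability arithmetic is firm. The step from predictability to bias is a possibility only: selective enrolment could distort the day-15 odds ratio, and a model with only site and age could not be relied on to correct it.

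**What to change.** In SAP 2.6, replace the single block of 3 with centrally generated permuted blocks of randomly varying size, in multiples of 3 (for example 3 and 6, or 6 and 9), within the same site and age strata. State that the sizes are held in a restricted document not available to sites, and leave them out of the SAP text if sites can see it. Of the two examples, 6 and 9 does somewhat better on both certainty and guessing.

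If enrolment has already begun, apply the new scheme to future allocations only. Add a comparison of baseline severity by position in block for patients already randomized, as a check on whether selection is visible.

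The cost is a new list, which means replacing a live one if randomization is running, and slightly more possible imbalance in small strata. Within a stratum, an unfinished block of 3 can leave two arms differing by at most 1 patient; a block of 6 allows 2, and a block of 9 allows 3. The primary model already adjusts for site and age. Some guessability will remain while the stage is open label and site is a blocking stratum.

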3. STATISTICAL CONSIDERATIONS

Data will be handled and processed per the sponsor's representative (Novotech) Standard Operating Procedures (SOPs), which are written based on the principles of good clinical practice (GCP).

3.1 General Considerations

All data collected on the electronic case report form (eCRF) will be presented in the data listings and will be listed and sorted by treatment arm, participant number and visit, where applicable. All descriptive summaries will be presented by treatment group and scheduled visit/time point (where applicable).

Unless otherwise stated, the following methods will be applied:

- **Continuous variables:** Descriptive statistics will include the number of non-missing values (n), arithmetic mean, standard deviation (SD), median, minimum and maximum values.

The minimum and maximum values will be displayed to the same decimal precision as the source data, the arithmetic mean, SD and median values and other derived values will be displayed to one more decimal than the source data for the specific variable.

95% Confidence Intervals (CIs), mean differences (among treatments and from baseline) and adjusted means values will be displayed to one more decimal than the source data for a specific variable. P-values will be displayed to 3 decimal places.

The appropriate precision for derived variables will be determined based on the precision of the data on which the derivations are based, and statistics will be presented in accordance with the aforementioned rules.

- **Categorical variables:** Descriptive statistics will include counts and percentages per category. The denominator in all percentage calculations will be the number of participants in the relevant analysis population with non-missing data, unless specifically stated otherwise. Percentages will be displayed to one decimal place. Proportions will be displayed to 3 decimal places.

95% Confidence Intervals (CIs), difference in proportions, odds ratio's and other categorical parameters will be displayed to one decimal place for percentages. Proportions will be displayed to 3 decimal places. P-values will be displayed to 3 decimal places.

- **Repeat/unscheduled assessments:** Only values collected at scheduled study visits/time points will be presented in summary tables. If a repeat assessment was performed, the result from the original assessment will be presented as the result at the specific visit/time point. All collected data will be included in the data listings.
- **Assessment windows:** All assessments will be included in the data listings and no visit windows will be applied to exclude assessments that were performed outside of the protocol specified procedure windows.
- **Result display convention:** Results will be center aligned in all summary tables and listings. Participant identifiers visit and parameter labels may be left-aligned if required.
- **Date and time display conventions:** The following display conventions will be applied in all outputs where dates and/or times are displayed:

Date only: YYYY-MM-DD

Date and time: YYYY-MM-DD HH:MM

If only partial information is available, unknown components of the date or time will be presented as 'NK' (not known), i.e., '2016-NK-NK'. Times will be reported in military time.

- **Specific items in relation to multiple comparisons, missing values, coding of medical, AE and medications and inferential statistics are covered in each of the specialized sections.**

